6.2.1.2 Eliciting and Documenting Adverse Events

The investigator is responsible for ensuring that all AEs and SAEs are recorded in the eCRF and reported to SIGA by PPD. Adverse events and SAEs will be assessed from the first dose of study drug in Period 1 through the telephone call on Day 59 (+4 days).

At every study visit or assessment, subjects will be asked a standard question to elicit any medically related changes in their well-being. They will also be asked if they have been hospitalized, had any accidents, used any new medications, or changed concomitant medication regimens (both prescription and over-the-counter medications).

In addition to subject observations, AEs will be documented from any data collected on the AE page in the eCRF (eg, laboratory values, physical examination findings, and ECG changes) or other documents that are relevant to subject safety.

6.2.1.3 Reporting Adverse Events

All AEs reported or observed from the first dose of study drug in Period 1 through the follow-up telephone call on Day 59 (+4 days) will be recorded on the AE page in the eCRF. Information to be collected includes drug treatment, type of event, date and time of onset,

dosage, investigator-specified assessment of severity and relationship to study drug, date and time of resolution of the event, seriousness, any required treatment or evaluations, and outcome. Any AEs resulting from concurrent illnesses, reactions to concurrent illnesses, reactions to concurrent medications, or progression of disease states must also be reported.

All AEs will be followed until they are resolved or stabilized as determined by the investigator and/or medical monitor. These data will be reviewed on an ongoing basis by the study coordinator, the investigator, the medical monitor, and the ISM. This requirement indicates that for some events, follow-up may be required after the subject has completed study participation. These events will be reported by SIGA, as required, to the FDA.

Any medical condition that is present at the time that the subject is screened but does not deteriorate should not be reported as an AE. However, if it deteriorates at any time during the study, it should be recorded as an AE. Prior to this, medical conditions reported by subjects are considered medical history.

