6.2 SAFETY ASSESSMENTS AND ENDPOINTS

Safety and tolerability will be assessed by monitoring and recording of AEs, clinical laboratory test results (hematology, serum chemistry, pregnancy, and urinalysis), vital sign measurements (systolic and diastolic blood pressures, heart rate, respiratory rate, and body temperature), 12-lead ECG results, and physical examination findings. Adverse events will

be assessed from the time of the first dose of study drug in Period 1 until the follow-up telephone call on Day 59 (+4 days).

For all safety assessments, the investigator will determine whether results are clinically significant or not clinically significant. Clinical significance is defined as any variation in a result that has medical relevance and may result in an alteration in medical care (eg, active observation, diagnostic measures, or therapeutic measures). If a clinical significance change from baseline is noted, the result and reason for significance will be documented and an AE reported on the AE page in the subject's eCRF. The investigator will continue to monitor the subject until the result has reached the reference range or the result at screening, or until the investigator determines that follow-up is no longer medically necessary.

When procedures are overlapping and occurring at the same time point, the order of procedures should be ECG, vital sign measurements, and then blood collection, with the blood collection scheduled to occur at the nominal time point, unless dictated by other study events happening at that time, such as dosing requirements.

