The purpose of this statistical analysis plan (SAP) is to define the planned statistical analysis of the study data consistent with the study objectives. This SAP is written based on Protocol: SIGA-246-023, version 2.0, dated 27 January 2022.

2. Study Objectives

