General study descriptors, as in subject disposition, demographics, protocol deviations, and enrollment characteristics, will be summarized for all randomized subjects, regardless of treatment sequence. Otherwise, safety outcomes, as in adverse events, lab values, vital signs, and electrocardiogram measures, will be summarized by treatment. The treatments below will be used for such presentation:

- TPOXX
- TPOXX + Sevelamer Carbonate
- TPOXX + Sucroferric Oxyhydroxide
- TPOXX + Calcium Acetate
- TPOXX + Lanthanum Carbonate

All data listings will be sorted by treatment and subject number.

No algorithm for imputation of missing data will be employed. Missing data will be treated as missing. If partial data exists for concomitant medications, the start dates will be imputed to the first of the month (for missing day) or first of the year (for missing day and month) for purposes of assigning a prior mediation flag.

There are no plans to derive visit windows; visits will be used in the analyses as reported on the eCRF.

Study days are calculated with respect to the first dose date as below:

- If the assessment/observation date is on or after the first dose date, then Study Day = Assessment/Observation Date First Dose Date + 1;
- Otherwise, Study Day = Assessment/Observation Date First Dose Date

Baseline will be defined as the day the subject checks in (Day -1) before the first dose of study drug administration, unless otherwise specified.

For summary of safety assessments, if there are repeated measurements at a time point, the first non-missing assessment at that time point will be used in the summary tables.

Unscheduled results will not be included in the summary tables, except for determining Baseline, but will be presented in data listings.

The methodology and data handling specifications for PK data are detailed in Section 8.

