9.1 Adverse Events

An AE is defined as any untoward medical occurrence, including those AEs that result from dosing errors, which may present during administration of a study drug or during a reasonable follow-up period and which does not necessarily have a causal relationship with the study drug(s). All AEs reported or observed from the first dose of study drug in Period 1 through the Day 36 End of Study Visit will be recorded on the AE page in the eCRF.

All AEs will be followed until the AE is resolved or stabilized as determined by the investigator and/or the medical monitor. Subjects will be instructed to contact the investigator at any time after randomization if any symptoms develop.

A serious AE (SAE) is defined as any AE that results in any of the following outcomes: death, a life-threatening AE, inpatient hospitalization or prolongation of existing hospitalization, a congenital anomaly or birth defect, a persistent or significant incapacity or substantial disruption of the ability to conduct normal activities of daily living. Important medical events that may not result in death, be life threatening, or require hospitalization may be considered serious when, based upon appropriate medical judgment, they may jeopardize the subject and may require

medical or surgical intervention to prevent one of the outcomes listed in this definition. All SAEs reported or observed from the first dose of study drug in Period 1 through follow-up telephone call on Day 59 (+4 days) will be recorded on the AE page in the eCRF.

In addition, the investigator (or designee) must report any Grade 3 (severe) AE that they deem possibly, probably, or definitely related to study drug to the medical monitor and SIGA within 24 hours after becoming aware of the event.

The AE's relationship to study treatment will be evaluated by the investigator. The following relationships will be collected on eCRF: definitely related, probably related, possibly related, unlikely related, or not related.

The AEs that are evaluated as definitely, probably, or possibly related will be considered treatment-related AEs for summary purpose.

The severity of AEs will be classified by the investigator as mild, moderate, severe, life threatening, or death.

An overall AE summary will be generated presenting the frequency and percentage of subjects and the number of AEs for the following:

- Any AE
- Any treatment-related AE
- Any moderate AE
- Any treatment-related moderate AE

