- Any treatment-related severe AE
- Any SAE
- Any treatment-related SAE
- Any AE leading to early discontinuation
- Any death

All AEs will be coded using MedDRA (version to be delineated in the CSR). The AEs will also be summarized by system organ class (SOC), preferred term (PT), by severity and relationship to study treatment.

The AE summary tables will be sorted by SOC and PT. System organ class will be displayed in descending order of overall frequency then alphabetically. Preferred term will be displayed in descending order of overall frequency and then alphabetically within SOC. A subject with 2 or more events within the same level of summarization will be counted only once in that level using the most severe incident or most related incident. Percentages will be based on the number of subjects in the safety population.

In summaries of AEs by treatment, AEs will be summarized according to the most recent treatment received prior to the AE onset. For example, an AE that occurred on or after

administration of the study drug on Day 1 of Period 1 but before the administration of study drug on Day 1 of Period 2 will be summarized for study drug administered in Period 1. All AEs will be presented in a data listing. Separate data listings will be generated for treatment-related AEs, SAEs, and AEs leading to study discontinuation.

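### The protocol collects all adverse events to Day 59, but SAP 9.1 stops non-serious events at Day 36, and its attribution rule sets no end for the last treatment

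*Combined protocol and SAP*

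**What the plan says.** **Protocol, collection of all AEs to Day 59.** Under Section 6.2, AEs are to "be assessed from the time of the first dose of study drug in Period 1 until the follow-up telephone call on Day 59", with a window of 4 further days. Section 6.2.1.2 gives the same period for AEs and SAEs together. Section 6.2.1.3 puts on the eCRF AE page "All AEs reported or observed from the first dose of study drug in Period 1 through the follow-up telephone call".

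**Protocol, the call described as being for SAEs.** The synopsis, Section 3 and Section 6.2.1.4 give SAE reporting as the purpose of the Day 59 call. Table 9-2 has separate rows for AEs and SAEs.

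**SAP 9.1.** For AEs, the eCRF AE page takes "All AEs reported or observed from the first dose of study drug in Period 1 through the Day 36 End of Study Visit". For SAEs, the same page takes "All SAEs reported or observed from the first dose of study drug in Period 1 through follow-up telephone call on Day 59", with the same window. On versions, SAP 1 states: "This SAP is written based on Protocol: SIGA-246-023, version 2.0, dated 27 January 2022".

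**Attribution and display.** SAP 9.1 adds that "AEs will be summarized according to the most recent treatment received prior to the AE onset". Its example closes a treatment's window only by the next dose. On denominators it says: "Percentages will be based on the number of subjects in the safety population". SAP 4 says that "safety outcomes, as in adverse events, lab values, vital signs, and electrocardiogram measures, will be summarized by treatment", and Protocol 7.3.2 also summarizes AEs by treatment and overall.

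**The concern.** Two instructions for the same eCRF page cannot both be followed. A non-serious AE that starts between the end-of-study visit and the Day 59 call is recordable under three protocol sections and outside the recording period in the SAP. The SAP cites the same protocol version, so a version difference does not explain it. The gap has practical consequences: Protocol 6.2.1.2 has subjects asked about changes in well-being at every visit or assessment, so the call may well bring up non-serious events.

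The attribution rule then decides where such an event is counted. TPOXX alone is always given in Period 1 and its window is closed by the Period 2 dose. The Period 5 treatment is always a binder and its window is closed by nothing except the end of collection. If collection runs to Day 59, the binder columns cover more time than the TPOXX-alone column, and percentages based on subject counts do not adjust for that. Safety and tolerability with the binders is the secondary objective, and TPOXX alone is the natural reference column in these tables.

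**Working it through.** **Inputs.** Doses on Days 1, 8, 15, 22 and 29 (schedules of events, 7-day interval). Sequences ABCDE, ACEBD, ADBEC and AEDCB in equal allocation (Protocol 5.3). Enrolment of 44, hence 11 per sequence. End-of-study visit 7 days after the last dose with a +2 day window, and call 30 days after the last dose with a +4 day window (Table 9-2). Assumption: all 44 complete.

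**Step 1: reproduce the plan's dates.** 29 + 7 = Day 36 and 29 + 30 = Day 59, as stated. With the windows, Day 38 and Day 63.

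**Step 2: which treatment comes last.** The last treatments of the four sequences are E, D, C and B. Each binder is last in one sequence (11 subjects) and in Periods 2 to 4 in the other three (33 subjects). TPOXX alone is never last in a completer.

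**Step 3: days attributed to each treatment under the most-recent-treatment rule.** TPOXX alone = 44 × 7 = 308 subject-days. Each binder = 33 × 7 + 11 × L, where L is the number of days from the last dose to the end of collection.

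| End of collection | L | Each binder | TPOXX alone | Ratio |
|---|---|---|---|---|
| Day 36 | 7 | 231 + 77 = 308 | 308 | 1.00 |
| Day 38 | 9 | 231 + 99 = 330 | 308 | 1.07 |
| Day 59 | 30 | 231 + 330 = 561 | 308 | 1.82 |
| Day 63 | 34 | 231 + 374 = 605 | 308 | 1.96 |

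Days 36 to 59 add 11 × 23 = 253 subject-days to each binder, 45% of its 561, and none to TPOXX alone.

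**Step 4: which row applies to which events.**
- SAP 9.1 as written: non-serious AEs follow the Day 36 or Day 38 row; SAEs follow the Day 59 or Day 63 row.
- Protocol 6.2, 6.2.1.2 and 6.2.1.3 combined with the SAP's attribution rule: all AEs follow the Day 59 or Day 63 row.

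**Step 5: sensitivity to dropout.** With 36 completers, 9 per sequence, and no partial data, the Day 59 ratio is unchanged: 27 × 7 + 9 × 30 = 459 against 36 × 7 = 252, or 1.82. As an assumed extreme, let 8 further subjects stop after Period 1 and be followed for 30 days. TPOXX alone then has 252 + 8 × 30 = 492 days, and the ratio is 459/492 = 0.93. The direction of the imbalance therefore depends on completion.

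**The case against.** The strongest reply is that the SAP which contains the open-ended rule also stops non-serious AEs at Day 36, so it largely removes the imbalance by itself. That stands. A reader might infer from the ratio of 1.82 that the binder columns of the AE tables will be inflated by that factor. The documents do not support this. The figure applies to all AEs only if the protocol's collection text is joined to the SAP's attribution rule. It counts days, not events; no AE or SAE rate is given, and nothing suggests that risk after a single dose stays constant for 30 days.

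A reader might also infer that the SAP simply departs from the protocol. It does not: SAP 9.1 agrees with the protocol sections that describe the call as being for SAEs. The change history also points to Day 36 for AEs in Table 9-2. It is used here only as a sign of the intended date, because the arrows in that table could not be read reliably in the text available.

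It is also fair to say that equal days are not equal ascertainment: Period 1 is spent wholly in the clinic, while Period 5 includes discharge on Day 31. Further, the tables are descriptive with no between-treatment test planned, SAEs are listed individually, and investigator causality is summarized. Whether late SAEs should leave the treatment columns is a presentation choice on which statisticians may differ. These points limit the size of the problem. They do not settle the conflicting cut-offs or supply the missing end of the last window.

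**Conclusion.** The main finding is an unresolved cut-off for non-serious AEs: Day 59 (+4) in Protocol 6.2, 6.2.1.2 and 6.2.1.3, Day 36 in SAP 9.1, with the protocol also divided on the purpose of the call. It should be corrected, since it determines what is recorded and tabulated.

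The open-ended attribution rule is secondary. With 44 completers, 11 per sequence, each binder column would cover 1.82 times the subject-days of TPOXX alone if all AEs ran to Day 59, and up to 1.96 times at Day 63. At the SAP's Day 36 cut-off the ratio is 1.00, or at most 1.07, and only SAEs with onset after the end-of-study visit remain affected. No event count can be derived. The consequence is limited to descriptive safety tables, and the PK primary objective is untouched.

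**What to change.** 1. Reconcile Protocol 6.2, 6.2.1.2 and 6.2.1.3, Table 9-2 and SAP 9.1 so that they state one cut-off for non-serious AEs and one for SAEs, and apply it in the AE tables. Day 36 and Day 59 would match SAP 9.1 and the stated purpose of the call.
2. In SAP 9.1, limit the by-treatment AE comparison to events with onset before the next dose or, for the last treatment received, within a comparable window of about 7 days after that dose. For completers this is the Day 36 visit. For subjects who withdraw, do not end the window at an early termination visit, which could fall less than 7 days after the last dose.
3. Identify later SAEs as follow-up events, in the tables or in the listings, and keep them in the overall total.

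**Cost.** Text edits to three protocol sections and, if needed, the schedule; one attribution sentence in a SAP still marked as a draft; and either a flag in the listings or one extra column in up to five AE tables (14.3.1.1 to 14.3.1.5). If late SAEs are taken out of the treatment columns, Protocol 7.3.2 and the synopsis need a matching clause. The drawback is that those SAEs would then be seen only as follow-up events, in the overall total and in the listings.

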6.2.1.4 Reporting of Serious Adverse Events

Any AE considered serious by the investigator or which meets SAE criteria (Section 6.2.1.1), or any other event or condition regardless of grade, which in their judgment represents a reportable event, must be reported to the medical monitor and SIGA as soon as the investigator becomes aware of the event. In addition, the event must be reported to PPD via the SAE hotline. The PPD SAE Report Form must be submitted within 24 hours of knowledge of the event. SIGA will be responsible for notifying the relevant regulatory authorities of any SAE as outlined in US Title 21 Code of Federal Regulations (CFR) Parts 312 and 320. The investigator is responsible for notifying the institutional review board (IRB) directly.

In addition, the investigator (or designee) must report any Grade 3 (severe) AE that they deem possibly, probably, or definitely related to study drug to the medical monitor and SIGA within 24 hours after becoming aware of the event.

After notification from the investigator, SIGA will report all study drug-related and unexpected SAEs (those not listed in the TPOXX full prescribing information) to the FDA within 15 calendar days of first knowledge. Fatalities or life-threatening events assessed as related and unexpected will be reported to the FDA within 7 calendar days of first knowledge. The ISM will also receive these reports.

For this study, the following contact information will be used for SAE reporting:

Medical Monitor:

The collection and monitoring period for SAEs is 30 days after administration of the last dose of study drug. At the time of discharge or early termination from the study site, the subject will be instructed to notify the investigator of any SAEs that occur within 30 days after the last dose of study drug.

All subjects will have a follow-up telephone call 30 days after administration of the last dose of study drug (Day 59 [+4 days]) to report any SAEs.

6.2.1.5 Assessment of Severity

All AEs will be graded for intensity according to the current DAIDS Table for Grading the Severity of Adult and Pediatric Adverse Events Version 2.1 July 2017.⁵

Any laboratory or clinical AE that is not listed on the DAIDS Table will be assessed for severity and classified into 1 of 5 clearly defined categories as follows:

- Grade 1 (Mild): Events require minimal or no treatment and do not interfere with the subject's daily activities.
- Grade 2 (Moderate): Events result in a low level of inconvenience or concern with the therapeutic measures and may cause some interference with normal functioning.
- Grade 3 (Severe): Events interrupt a subject's usual daily activity, may require systemic drug therapy or other treatment, and are usually incapacitating.
- Grade 4 (Life-threatening): Event that, in the opinion of the investigator, places the subject at immediate risk of death from the reaction as it occurred (ie, it does not include a reaction that, had it occurred in a more severe form, might have caused death).
- Grade 5 (Death).

Changes in the severity of an AE should be documented to allow an assessment of the duration of the event at each level of intensity to be performed. An AE characterized as intermittent requires documentation of the onset and duration of each episode.

6.2.1.6 Assessment of Causality

Any occurrence of an AE will be assessed for relationship to the study drug. A causal relationship means that the study drug caused (or is reasonably likely to have caused) the AE. This usually implies a relationship in time between the study drug and the AE; for example, the AE occurred shortly after the subject received the study drug.

The investigator who examines and evaluates the subject will determine AE causality based on the temporal relationship to administration of the study drug, the pharmacology of the study drug, and their clinical judgment. Terms used to describe the degree of causality between each study drug and an AE are definitely related, probably related, possibly related, unlikely related, or not related.

The best estimate at the time of reporting of an event and the degree of certainty about the causal relationship between the study drug administration and the AE will be graded as follows:

Associated

- Definitely Related: The AE and administration of study drug are related in time, and a direct association can be demonstrated (eg, the event disappears or decreases with reduction in dose or cessation of study drug and recurs with re-exposure).
- Probably Related: The AE and administration of study drug are reasonably related in time and/or follow a known pattern of response, and the AE is more likely explained by study drug than other causes.
- Possibly Related: The AE and administration of study drug are reasonably related in time and/or follow a known pattern of response, but the AE can be explained equally well by causes other than study drug (eg, could readily have been produced by the subject's clinical state or could have been due to environmental or other interventions).

Not Associated

• Unlikely Related: A potential relationship between study drug and the AE could exist (ie, the possibility cannot be excluded), but the AE is most likely explained by causes other than the study drug (eg, could readily have been produced by the subject's clinical state or could have been due to environmental or other interventions).

• Not Related: The AE is clearly due to extraneous causes (eg, underlying disease, environment) or exposure to the study drug has not occurred. Such events MUST have an alternative, definitive etiology documented in the subject's medical record.

